# 4.3.2. Secondary Outcome Measures:

- 1. Percentage of subjects who survive 90 days after HPE with both their native liver and serum total bilirubin <1.5 mg/dL at 90 days after HPE. For this study, serum total bilirubin must be measured as a total and not calculated by summing bilirubin components (such as serum indirect plus direct bilirubin or conjugated plus unconjugated bilirubin).
- 2. Percentage of subjects who survive 180 days after HPE with both their native liver and serum total bilirubin <1.5 mg/dL at 180 days after HPE. For this study, serum total bilirubin must be measured as a total and not calculated by summing bilirubin components (such as serum indirect plus direct bilirubin or conjugated plus unconjugated bilirubin).
- 3. Percentage of subjects who survive 360 days after HPE with both their native liver and serum total bilirubin concentration <1.5 mg/dL at 360 days after HPE.
- 4. Percentage of subjects who survive with their native liver at 360 days after HPE.
- Percentage and absolute number of Tregs (CD4+CD25+FoxP3+), CD3/4 T cells, CD3/8 T cells, NK cells (CD56), NK T cells (CD3/56), CD19/20 B cells, macrophages (CD14/11b), and neutrophils; plasma levels of anti-enolase antibody; and plasma cytokine levels (Th1/Th2 multiplex and IL17) prior to IVIG dose #1 and at 60, 90, 180, and 360 days after HPE.

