# 4.7.6. Routine childhood immunizations

It is expected that routine primary immunizations will be given to all children by their primary care provider as recommended by the Committee on Infectious Diseases of the American Academy of Pediatrics (AAP). IVIG has been shown to interfere only with live virus vaccines but not killed virus vaccines. Only killed virus vaccines will be administered to infants under one year of age in this trial. Participants may receive live attenuated viral vaccines at 12-15 months of age (MMR and Varicella vaccinations) because it is very unlikely that substantial amounts of IVIG would still be circulating in the participant at that time. This is based on the last IVIG dose being given 60 days after the HPE procedure, the latter which is expected to be performed at 40 to 100 days of age in the majority of participants with the latest it can be performed in this trial being 180 days of age. The Rotavirus vaccines (live attenuated virus vaccines) are not recommended in children with significant abdominal disorders or following abdominal surgery, and therefore are not recommended for study participants.

Development of infectious diseases and vaccine-preventable diseases Subjects will be prospectively monitored for the development of infectious diseases and vaccine-preventable diseases. Parents and primary care providers of all enrolled subjects will be instructed to contact the study coordinator promptly at the time of any infectious acute illness that leads to visit to the primary care provider, to an emergency department, or if the subject requires hospitalization. An Adverse Event Form will be completed within 24 hrs of each report.

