# 5.2.2. Preliminary Efficacy (Activity).

The use of concurrent placebo or active control subjects was considered for this study, however it is not feasible to treat infants in a research study with an IV placebo (normal saline) and the availability of robust patient-level data for historical controls from another ChiLDREN study were felt to justify the bias issues inherent in the use of historical controls.

Placebo subjects from the ChiLDREN START (Steroids in Biliary Atresia Randomized Trial) study will be used as a historical comparative group to compare with subjects in this study who receive IVIG. Approximately 70 subjects in START received placebo from 2006-2011, but were otherwise treated similarly to the subjects in the current trial, except they received no IVIG. It is anticipated that the START randomized double-blind study will be unblinded in early 2013. With the anticipated length of this IVIG study (24-30 months enrollment and 12 months of follow-up), we will be able to use the START placebo subjects as the comparative group.

A one-sided testing strategy was chosen given that we are only interested if IVIG improves the preliminary measures of efficacy.

Hypothesis 2a states that treatment with IVIG will improve the probability of an infant having good bile flow 90 and 180 days after HPE for BA as evidenced by total serum bilirubin concentration. The primary endpoint for this hypothesis is the proportion of subjects who survive 180 days after HPE with both their native liver and serum total bilirubin <1.5 mg/dL at 180 days after HPE. Based on the ChiLDREN PROBE prospective study, approximately 51% of BA subjects who had an HPE before 4 months of age had good bile drainage at 6 months following the HPE procedure, as determined by a serum total bilirubin level <1.5 mg/dL and survival with their native liver. We anticipate the same improvement in the placebo subjects in the ChiLDREN START study.

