Assuming 20% loss-to-follow-up in the ChiLDREN START study and in this study (i.e., 23 subjects in the IVIG group and 56 subjects in the START placebo group), there is 74% power with a one-sided Type I error rate of 10% to detect a difference of 25.5% -- a 50% improvement with treatment (i.e., 76.5% in the IVIG group and 51% in the placebo group). This is based on Fisher's exact test for two proportions (SAS 9.3). The corresponding power for sample sizes of 29 and 70 in the IVIG and placebo groups (if there were no drop-outs) is 82%. Alternatively, we have 80% power to detect a difference of 28% in this outcome (79% in the IVIG group and 51% in the placebo group) with sample sizes of 23 and 56 in the IVIG and placebo groups, reflecting a possible 20% drop-out rate. The corresponding power for sample sizes of 29 and 70 in the IVIG and placebo groups, if there were no drop-outs, is 88%.

Hypothesis 2b states that treatment with IVIG will improve the probability of an infant having good bile flow 360 days after HPE for BA as evidenced by the proportion of subjects who survive 360 days after HPE with both their native liver and serum total bilirubin <1.5 mg/dL at 360 days after HPE. In the prospective PROBE study, approximately 68% of BA patients who had an HPE by 4 months of age survived to 12 months of age with their native liver and had serum bilirubin <1.5 mg/dL. We assume that a comparable proportion of placebo subjects in START will have this outcome. There is 76% to 85% power to detect a 33% relative improvement in this outcome with the anticipated sample sizes described above (ranging from 23 and 56 in the IVIG and placebo groups, respectively, when adjusting for 20% drop-out, to 29 and 70 in the IVIG and placebo groups, respectively, if there were no drop-out), based on Fisher's exact test for two proportions (SAS 9.3) and a one-sided Type I error rate of 10%. This relative

improvement corresponds to approximately 90% of the IVIG subjects having improved bile flow at 360 days after HPE, compared to an anticipated 68% in START placebo patients.

Hypothesis 3 states that survival with native liver at 360 days following HPE is improved in infants treated with IVIG compared to historical controls. Since 68% of PROBE BA patients who had their HPE by 4 months of age survived to 12 months of age with their native liver and with serum total bilirubin < 1.5 mg/dL, the power calculations for Hypothesis 2b apply identically to Hypothesis 3.

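### The Hypothesis 3 power is borrowed from a stricter endpoint's control rate, so the stated 76–85% is unsupported for native-liver survival at 360 days

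*Protocol*

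**What the plan says.** Section 4.3.2 lists two separate 360-day outcomes. One is survival with native liver and total bilirubin below 1.5 mg/dL (Hypothesis 2b). The other is "Percentage of subjects who survive with their native liver at 360 days after HPE", with no bilirubin condition (Hypothesis 3).

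For Hypothesis 2b, section 5.2.2 reports that in PROBE about 68% of infants with HPE by 4 months of age "survived to 12 months of age with their native liver and had serum bilirubin <1.5 mg/dL". It assumes the same for START placebo subjects and concludes: "There is 76% to 85% power to detect a 33% relative improvement in this outcome". The sample sizes are 23 IVIG and 56 control subjects after 20% loss, or 29 and 70 with none. The test is Fisher's exact test at one-sided 10%, and the IVIG rate is about 90%.

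For Hypothesis 3, the same section cites that 68% again, still with the bilirubin condition attached, and gives it as the reason that "the power calculations for Hypothesis 2b apply identically to Hypothesis 3". The protocol gives no rate for native-liver survival alone.

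**The concern.** Infants who meet the Hypothesis 2b outcome are a subset of those who meet the Hypothesis 3 outcome. A power statement for the wider outcome cannot rest on the control rate of the narrower one, and the reason the protocol gives for the transfer is exactly that rate.

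Two further features do not carry over. The 68% is measured at 12 months of age, whereas both outcomes are at 360 days after HPE. The quoted power is for Fisher's test, whereas section 5.3 (Aim 3) analyses Hypothesis 3 as a difference between Kaplan-Meier estimates.

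At stake is a stated design property of a secondary aim. Section 2.4 says the results should help decide whether a larger trial is worth running, and a reader weighing the native-liver result would take 76–85% as the chance of having detected a 33% relative gain.

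**Working it through.** **Inputs.** From section 5.2.2: control rate 68%; relative gain 33%; sample sizes 23/56 and 29/70; Fisher's exact test, one-sided 10%. The native-liver-only control rates used below (75%, 80%) are assumptions, because the protocol gives none.

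**Method.** Reject when the hypergeometric tail P(X ≥ x | x + y) ≤ 0.10. Power = Σₓ Σᵧ Bin(x; n₁, p₁) · Bin(y; n₀, p₀) over the rejected pairs (x, y).

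**1. Reproduce the stated figure.** 0.68 × 1.33 = 0.9044. Power for 68% against 90.44% is 76.4% (23/56) and 85.7% (29/70); with exactly 90% it is 74.5% and 84.1%. The protocol states 76% to 85%. The same method gives 74.3% and 82.2% for Hypothesis 2a at 51% against 76.5% (stated 74% and 82%). The method is therefore right, and the Hypothesis 2b figure stands on its own inputs.

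**2. The two control rates.** Let C be the composite rate, N the native-liver survival rate at the same time, and q the share of native-liver survivors with bilirubin below 1.5 mg/dL. Then C = N × q, so N = C/q, and N = C only if q = 1. The diet table in section 4.7.2 has a row for children of 12 months or older with bilirubin at or above 1.5 mg/dL, so the protocol does not expect q = 1. Taking C = 68%, N = 75% corresponds to q = 0.68/0.75 = 0.91, and N = 80% to q = 0.68/0.80 = 0.85.

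**3. Hypothesis 3 power by Fisher's test, at assumed control rates.** The odds ratio implied by 68% against 90% is (0.90/0.10)/(0.68/0.32) = 4.24. Applied to 75% (odds 3) it gives odds of 12.7, that is 92.7%; applied to 80% (odds 4), 94.4%. The absolute gain is 90 − 68 = 22 points.

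| Control | IVIG | Effect held constant | 23/56 | 29/70 |
|---|---|---|---|---|
| 75% | 90% | IVIG rate | 49% | 60% |
| 80% | 90% | IVIG rate | 29% | 37% |
| 75% | 92.7% | odds ratio | 63% | 75% |
| 80% | 94.4% | odds ratio | 52% | 65% |
| 75% | 97% | +22 points | 87% | 95% |

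The stated effect has a ceiling: 1/1.33 = 75.2%, so above a control rate of about 75% a 33% relative gain would need an IVIG rate over 100%.

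**4. The planned analysis.** With no censoring, Greenwood's standard error reduces to √(p(1−p)/n). The Kaplan-Meier comparison then becomes a Wald difference, read here as favouring IVIG when (p̂₁ − p̂₀) − 1.2816 × √(p̂₁(1−p̂₁)/n₁ + p̂₀(1−p̂₀)/n₀) > 0. Summed over the same binomials, power is 89% and 92% for 68% against 90.4%, 70% and 74% for 75% against 90%, and 52% and 56% for 80% against 90%. Part of the gain over Fisher is excess type I error: with both rates at 75%, the same sum rejects 13.4% (23/56) and 11.5% (29/70) of the time, against a nominal 10%.

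**5. The time point.** Section 4.7.6 has HPE "expected to be performed at 40 to 100 days of age in the majority of participants". Twelve months of age is then about day 365 − 100 = 265 to day 365 − 40 = 325 after HPE, which is 35 to 95 days short of day 360. Native-liver survival can only fall over that gap, so this mismatch pulls the Hypothesis 3 rate down while dropping the bilirubin condition pulls it up. The document does not size the gap.

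**6. Consistency of the 68%.** Section 5.2.2 also says that about 51% of PROBE infants "had good bile drainage at 6 months following the HPE procedure", by the same composite definition. The later figure is 68 − 51 = 17 points higher. Whether that reflects late clearance of jaundice, a different denominator or a mislabelled endpoint cannot be told from the protocol.

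**The case against.** The strongest reply is that the aim is secondary, seeks only preliminary evidence, and does not drive the design: section 5.2 sizes the trial primarily on precision for feasibility, tolerability and safety. No outcome, analysis or sample size depends on the sentence. That stands. It limits the weight of the point and does not make the sentence right.

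Three stronger readings are tempting and should be resisted.

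- A reader might infer that the trial is weak for Hypothesis 3. That holds if IVIG stays at 90%, but keeping the 22-point gain at a 75% control rate gives 87–95%, above the stated range. The planned Kaplan-Meier difference also has higher nominal power than Fisher's test at the same rates.
- A reader might infer from 51% and 68% that the 68% is really native-liver survival, so that the Hypothesis 2b power is the wrong one. The protocol twice defines the 68% with the bilirubin condition, and the PROBE denominators are not shown. A 33% gain from 51% would have about 44–52% power, but for a 51% control rate the protocol itself assumes a 50% gain, with 74–82%. The 51% is in any case a 6-month rate.
- A reader might say that the two power statements cannot both hold. They could in one degenerate case, where every native-liver survivor has bilirubin below 1.5 mg/dL.

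**Conclusion.** The concern holds in a limited form. The 76–85% is correct arithmetic for a 68% control rate against about 90% and is unsupported for Hypothesis 3, whose control rate is not given. Nothing else in the protocol repairs the transfer. At assumed control rates of 75% and 80%, Fisher power runs from 29% to 95% depending on the control rate, the effect held constant and the amount of drop-out; the uncensored Wald approximation gives 70–74% and 52–56% against a 90% IVIG rate. These figures show how far the answer moves. They do not estimate the true power. What is firm is that the borrowed power lacks a basis, and that the borrowed 33% relative gain becomes unattainable once the control rate passes about 75%. This should be corrected, but it does not threaten the trial's primary aim.

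**What to change.** In section 5.2.2:

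1. Delete the statement that the Hypothesis 2b calculations carry over to Hypothesis 3.
2. Tabulate from PROBE two rates at 360 days after HPE: native-liver survival, and native-liver survival with total bilirubin below 1.5 mg/dL. START placebo data would serve if available, but the protocol only anticipates unblinding in early 2013 (5.2.2) and elsewhere says the results may arrive before this trial is complete (6.1.6), so it does not show that they are in hand.
3. Confirm which endpoint the 68% describes, in view of the 51% at 6 months after HPE.
4. Restate the Hypothesis 3 power separately, with an effect size attainable at its own control rate and for the planned Kaplan-Meier difference. If the rate remains uncertain, give the power over a range.

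Leave the sample size unchanged. The cost is one tabulation from a study the network already runs, a short recalculation and a replaced paragraph. The restated power may be lower or higher than 76–85%.

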# Aim 3: To obtain preliminary evidence whether IVIG treatment after HPE will improve survival without liver transplantation at 360 days after HPE.

**Hypothesis 3:** Survival without transplantation will be greater at 360 days after HPE in infants treated with IVIG compared to historical controls.

The proportion of subjects who have survived with their native liver at 360 days after HPE will be estimated among the IVIG treated subjects and the historical placebo controls by Kaplan-Meier methods. Time to liver transplantation or death will be calculated as the number of days from the day of HPE to the first of liver transplantation, death, or last day of follow-up without these events. Subjects will be censored if these events don't occur by the last day of study follow-up. The difference between the two Kaplan-Meier estimates will be computed and a 90% upper confidence bound will be calculated for the difference, using the pooled variance (based on each group's standard error calculated with Greenwood's formula).

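### The power quoted for Hypothesis 3 is that of a Fisher test, but the plan analyses Hypothesis 3 with a Kaplan-Meier difference and a Greenwood-based bound whose power and error rate differ

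*Protocol*

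**What the plan says.** In Protocol section 5.2.2 the Hypothesis 2b calculation is "based on Fisher's exact test for two proportions (SAS 9.3) and a one-sided Type I error rate of 10" per cent. The control rate comes from PROBE, where "approximately 68% of BA patients who had an HPE by 4 months of age survived to 12 months of age with their native liver"; the same figure also requires bilirubin below 1.5 mg/dL. The result is given as "There is 76% to 85% power to detect a 33% relative improvement in this outcome with the anticipated sample sizes described above", the sizes "ranging from 23 and 56 in the IVIG and placebo groups, respectively, when adjusting for 20% drop-out" and 29 and 70 without drop-out. The target is "approximately 90% of the IVIG subjects having improved bile flow at 360 days after HPE". The section then states for native-liver survival that "the power calculations for Hypothesis 2b apply identically to Hypothesis 3". Earlier it sets the framework for all the efficacy measures: "A one-sided testing strategy was chosen given that we are only interested if IVIG improves the preliminary measures of efficacy".

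Section 5.3, Aim 3, describes a different analysis. The 360-day proportions are "estimated among the IVIG treated subjects and the historical placebo controls by Kaplan-Meier methods". Infants without an event are censored at their last follow-up. The two estimates are subtracted and a 90% upper confidence bound is formed for the difference. Its variance is called pooled and is said to be based on each group's Greenwood standard error. The section does not say which group is subtracted from which, or what value of the bound would support Hypothesis 3.

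**The concern.** The protocol fixes both the powered method and the analysis method for Hypothesis 3, and they are not the same. The analysed set differs too: 23 and 56 are the group sizes after drop-outs are removed, whereas under Kaplan-Meier an infant who leaves early still contributes until censoring.

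With 23 to 29 treated infants and high survival, the choice of method matters. Fisher's test is conservative. A plain Greenwood normal bound tends to err the other way, because the IVIG standard error shrinks as survival approaches 100% and is zero if every infant survives. A borderline survival signal could therefore count as evidence of benefit under one method and not under the other. Section 2.4 says the results should help decide whether a larger trial is worthwhile, so the false-positive rate of that signal matters.

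**Working it through.** **Inputs (Protocol 5.2.2 and 5.3).** Control rate 68%; IVIG rate 68% × 1.33 = 90.4%; group sizes 23/56 and 29/70; one-sided 10%, critical value 1.2816.

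**Methods.** All pairs of binomial outcomes were enumerated exactly.
- Fisher: reject if the one-sided hypergeometric p ≤ 0.10.
- Planned bound: with no censoring before day 360, the Kaplan-Meier estimate is the simple proportion and Greenwood's variance is p(1−p)/n. With the two variances summed, benefit is shown if (p₁ − p₀) / √[p₁(1−p₁)/n₁ + p₀(1−p₀)/n₀] > 1.2816, where 1 is IVIG and 0 is control.
- Alternative reading of the word pooled: variance p̄(1−p̄)(1/n₁ + 1/n₀), where p̄ is the proportion in both groups combined.

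**Step 1: the protocol's figure reproduces.** Fisher power at 90.4% versus 68% is 76.4% (23/56) and 85.7% (29/70), in line with the stated 76% to 85%. At exactly 90% it is 74.5% and 84.1%.

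**Step 2: power of the planned analysis, same inputs.**

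| Method | 23/56 | 29/70 |
|---|---|---|
| Fisher | 76.4% | 85.7% |
| Summed Greenwood variances | 89.0% | 92.1% |
| Pooled-proportion variance | 85.5% | 91.4% |

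The gap between the first two rows is 89.0 − 76.4 = 12.6 points and 92.1 − 85.7 = 6.4 points. A simulation of the Kaplan-Meier analysis itself (20,000 runs, 29/70, exponential event times, 20% random drop-out) gave 89.2% at 90% versus 68%.

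**Step 3: one-sided error when both groups share one survival rate.** Each cell gives 23/56, then 29/70.

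| Common rate | Fisher | Summed Greenwood | Pooled proportion |
|---|---|---|---|
| 68% (protocol) | 6.1%, 6.3% | 12.6%, 11.6% | 10.1%, 10.2% |
| 80% (assumed) | 5.4%, 6.2% | 13.7%, 12.3% | 10.2%, 10.8% |
| 90% (assumed) | 3.4%, 4.2% | 16.7%, 15.4% | 9.9%, 9.5% |

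With 20% censoring at 29/70, the simulated error of the summed-Greenwood bound was 11.6% at 68%, 12.8% at 80% and 13.5% at 85%.

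**Step 4: a borderline table.** Take IVIG 20/23 (87.0%) and control 42/56 (75.0%), a difference of 0.1196.
- Summed Greenwood: standard error √(0.00493 + 0.00335) = 0.0910; z = 0.1196/0.0910 = 1.31, above 1.28, so benefit is shown.
- Pooled proportion: p̄ = 62/79 = 0.785; standard error 0.1018; z = 1.17, so benefit is not shown.
- Fisher: p = 0.19, not shown.

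At 21/23 all three show benefit (Fisher p = 0.087).

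**Step 5: a bound that holds 10%.** Each group's one-sided 90% limit is formed on the complementary log-log scale, with an exact limit if there are no events. The two are combined by square-and-add: lower limit = (p₁ − p₀) − √[(p₁ − l₁)² + (u₀ − p₀)²], where l₁ is the IVIG lower limit and u₀ the control upper limit. For common rates from 51% to 90% and both sizes the error is 6.3% to 9.4%. Power at 90.4% versus 68% is 81.8% (23/56) and 89.3% (29/70).

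**The case against.** Several points on the other side stand.

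- A reader might infer that the 76% to 85% belongs to neither method. That is not so: it is the Fisher power at the protocol's own inputs.
- A reader might also infer that the trial is shown to be weaker than claimed. At 68% versus 90.4% the stated figure understates the planned method's power.
- Error rates as far apart as 3% and 17% are tempting to quote, but they need a common survival near 90%. The only control rate in the protocol is 68%, where the contrast is about 6% against 12% to 13%. At 29/70 the excess over nominal is 1.6 points.
- The word pooled is ambiguous. A pooled-proportion variance would bring the error close to 10%. The reference to each group's Greenwood standard error makes summed variances the more natural reading, but the text does not settle it.
- Section 5.3 gives a bound and no decision rule, so its error rate is that of reading it as a test. The one-sided testing strategy in 5.2.2 makes that reading reasonable, but it remains a reading. An upper bound can show benefit only if the difference is control minus IVIG, which is not stated.
- Aim 3 is secondary and preliminary, and the trial is sized mainly on feasibility, tolerability and safety. A one-infant difference at the threshold would arise with any test at these sizes.

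These points limit the size of the problem. They do not make the two calculations identical.

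**Conclusion.** The point holds as a mismatch that should be corrected. The power quoted for Hypothesis 3 is not that of the analysis planned for it. At the protocol's inputs, without censoring and with summed Greenwood variances, the difference is about 6 to 13 points, and the stated figure is the lower one. Used as a one-sided 10% test, the planned bound runs at 11.6% to 12.6% at a common 68%, about twice Fisher's rate. The documents do not support a claim of gross error inflation.

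One limit applies to every power figure here. The 68% belongs to the composite with bilirubin below 1.5 mg/dL, at 12 months of age. Hypothesis 3 concerns native-liver survival alone at 360 days after HPE, and dropping the bilirubin condition can only raise the rate. At an assumed 80% versus 90%, power falls to 28.5% to 36.8% for Fisher and 51.6% to 55.7% for the summed-Greenwood bound. The finding that the planned power is higher than stated therefore holds at 68% versus 90.4% and should not be carried to other rates.

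**What to change.** In section 5.2.2, delete the statement that the Hypothesis 2b power carries over unchanged and give power for the Kaplan-Meier analysis of Hypothesis 3, with its censoring assumption. In section 5.3, Aim 3, state the direction of the difference, write out the variance formula, and say that the one-sided 90% bound decides Hypothesis 3.

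Use a bound that holds 10% at these sizes. Complementary log-log limits combined by square-and-add are one option and keep the Kaplan-Meier estimate.

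The cost is wording in two sections and one power calculation. Power falls against the plain Greenwood bound by 89.0 − 81.8 = 7.2 points at 23/56 and 92.1 − 89.3 = 2.8 points at 29/70. It stays above Fisher's 76.4% and 85.7%.

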# 4.7.2. Diet

When the total serum bilirubin is  $\geq 1.5$  mg/dL and the child is less than 12 months of age, MCT-containing formula or breast milk should be used, as long as the child's growth is "adequate". When the total bilirubin is <1.5 mg/dL, the child can be transitioned to standard infant formula (if <12 months of age) and whole milk (if  $\geq$  12 months of age) or breast milk can be continued if the preference of the family. MCT-containing formula or breast milk will

be continued if the total bilirubin is  $\geq 1.5$  mg/dL and the child is 12 months of age or older. When growth is inadequate, measures will be taken for nutritional rehabilitation according to medical management used at each ChiLDREN clinical center. Solid foods will be initiated at the discretion of the subject's primary care provider. MCT-containing formula will not be supplied or paid for by this study, since it is standard of clinical care.

Growth	Age (mo)	Total Bilirubin (mg/dL)	Diet
Adequate	<12	> 1.5	MCT-containing formula or breast milk
Adequate	<12	<1.5	Standard formula or breast milk
Adequate	> 12	> 1.5	MCT-containing formula [or breast milk]
Adequate	> 12	<1.5	Whole milk or breast milk
Inadequate	N/A	N/A	Nutritional rehabilitation

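### One PROBE rate (68%) is used as the control rate for two different 360-day endpoints, so the 76% to 85% power is unsupported for Hypothesis 3, or for Hypothesis 2b if the rate is mislabelled

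*Protocol*

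**What the plan says.** Section 4.3.2 lists two separate 360-day outcomes. Item 3, the Hypothesis 2b endpoint, reads "Percentage of subjects who survive 360 days after HPE with both their native liver and serum total bilirubin concentration <1.5 mg/dL at 360 days after" the operation. Item 4, the Hypothesis 3 endpoint, reads "Percentage of subjects who survive with their native liver at 360 days after HPE" and has no bilirubin condition. Section 1.2 (Aim 3) and section 5.3 (Aim 3) also define Hypothesis 3 without bilirubin.

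Section 5.2.2 gives one control rate for both. For Hypothesis 2b, about 68% of PROBE infants with HPE by 4 months of age "survived to 12 months of age with their native liver and had serum bilirubin <1.5 mg/dL". From this it derives the power: "There is 76% to 85% power to detect a 33% relative improvement in this outcome", the range running from 23 IVIG and 56 placebo infants (20% drop-out) to 29 and 70 (none). The effect is spelled out as "approximately 90% of the IVIG subjects having improved bile flow at 360 days after HPE, compared to an anticipated 68% in START placebo patients".

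For Hypothesis 3 the section cites the same 68%, again as infants who "survived to 12 months of age with their native liver and with serum total bilirubin < 1.5 mg/dL", and concludes that "the power calculations for Hypothesis 2b apply identically to Hypothesis 3". The protocol gives no rate for native-liver survival alone at 360 days.

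**The concern.** The reason given for carrying the power over is a rate for the composite, whereas Hypothesis 3 is about one component of it. Every infant who meets the composite also meets native-liver survival. An infant who has its own liver but is still jaundiced meets only the second. The two proportions are therefore different quantities unless no such infant exists.

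The protocol itself expects such children. Section 4.7.2 keeps "MCT-containing formula or breast milk" in the diet of children aged 12 months or older whose total bilirubin is 1.5 mg/dL or more. That guideline does not say how many there are.

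At stake is the reading of Aim 3. Sections 2.4 and 6.4 say the results should help decide whether a larger phase 2 or 3 trial is worthwhile. A reader who trusts 76% to 85% power will give a null native-liver result a weight that the document does not justify.

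**Working it through.** **Inputs** (section 5.2.2): control rate 68%; relative gain 33%; 23 vs 56 and 29 vs 70 infants; Fisher's exact test, one-sided 10%.

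**Method.** Exact power: enumerate every pair (x, y) of binomial outcomes, reject when the one-sided hypergeometric tail is at most 0.10, and sum the probabilities of the rejecting pairs.

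**Step 1: reproduce the plan.** The IVIG rate is 0.68 × 1.33 = 0.9044.

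| Control vs IVIG | Stated power | Recomputed, 23/56 and 29/70 |
|---|---|---|
| 51% vs 76.5% (Hypothesis 2a) | 74% and 82% | 74.3% and 82.2% |
| 51% vs 79% (Hypothesis 2a) | 80% and 88% | 81.6% and 88.5% |
| 68% vs 90.44% (Hypothesis 2b) | 76% and 85% | 76.4% and 85.7% |

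All agree to within 2 points. The calculation is sound; the question is which endpoint the input belongs to.

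**Step 2: relate the two endpoints.** At one time point,

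P(native liver) = P(native liver and bilirubin <1.5) + P(native liver and bilirubin ≥1.5).

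The two rates are equal only if the last term is zero. The protocol gives no value for that term.

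**Step 3: sensitivity.** The control rates above 68% below are assumptions, since the document supplies none. Two ways of carrying the effect over are shown, because section 5.2.2 describes it both as a 33% relative gain and as about 90% on IVIG.

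| Assumed control rate | Fixed 33% relative gain: IVIG rate; power 23/56, 29/70 | Fixed 90% on IVIG: power 23/56, 29/70 |
|---|---|---|
| 68% | 90.4%; 76%, 86% | 75%, 84% |
| 69% | 91.8%; 79%, 88% | not computed |
| 70% | 93.1%; 82%, 91% | 68%, 79% |
| 75% | 99.75%; 99%, >99% | 49%, 60% |
| 80% | 106.4%; impossible | 29%, 37% |

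The ceiling for a 33% relative gain is 1/1.33 = 75.2%. Above that control rate the effect in the plan cannot exist.

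**Step 4: sensitivity to one point.** With IVIG held at 90.44%, moving the control rate from 68% to 69% changes power from 76%/86% to 73%/83%. With the relative gain held at 33%, the same move gives 79%/88%. The two conventions move in opposite directions.

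**Step 5: time point.** The 68% refers to 12 months of age. Section 4.7.6 expects HPE at 40 to 100 days of age in most infants, so 360 days after HPE is about 400 to 460 days of age (40 + 360 to 100 + 360). Native-liver survival can only fall between the two times. The inequality in step 2 therefore makes 68% a lower bound for native-liver survival at 12 months of age, but not at the Hypothesis 3 time point.

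**The case against.** The strongest reply is that 68% may really be native-liver survival, with the bilirubin condition attached by mistake. Two things in the protocol make this plausible. The composite is given as 51% at 6 months after HPE but 68% at 12 months of age. Section 1 also says that over 50% of patients need a transplant by 2 years of age, which sits uneasily with 68% being both untransplanted and jaundice-free at 12 months. Neither is proof. On that reading the Hypothesis 3 control rate stands, and Hypothesis 2b is the one left without a valid rate. This limits the conclusion but does not remove it, because one rate still serves two endpoints.

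A reader might also infer three stronger things that the documents do not support:

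- **That the Aim 3 power is overstated.** At the plan's own 33% relative gain, a higher control rate raises power until the ceiling is reached. It falls only if the IVIG rate is held fixed.
- **That a 33% gain is impossible.** That requires a control rate above 75.2%, and nothing in the protocol shows one.
- **That native-liver survival at 360 days after HPE must be at least 68%.** The bound holds at 12 months of age only.

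Finally, the consequences are limited. Section 5.2 sizes the trial mainly on feasibility, tolerability and safety. Aim 3 is secondary and seeks preliminary evidence, and section 5.3 analyses it by estimation: a Kaplan-Meier difference with a 90% confidence bound. That stands, and it sets the severity.

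**Conclusion.** The point holds in this form: the 76% to 85% power is correctly computed for 68% against about 90.4%, but it cannot be carried to Hypothesis 3 on the reason given. It is unsupported for Hypothesis 3 if 68% is the composite, as written, or for Hypothesis 2b if 68% is native-liver survival mislabelled. Only the PROBE data can settle which.

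This rests on the endpoint definitions in section 4.3.2 and on there being some native-liver survivors with bilirubin of 1.5 mg/dL or more, whom the diet guideline foresees without counting. The size and direction of the error cannot be established from the document. The assumed control rates show only that the answer is sensitive: at 70%, power is anywhere from 68%/79% to 82%/91%, depending on which version of the effect is kept.

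This should be fixed. It does not affect the sample size of 29, the endpoints or the conduct of the trial.

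**What to change.** In section 5.2.2:

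1. Delete the statement that the Hypothesis 2b power carries over unchanged to Hypothesis 3.
2. From PROBE, tabulate two rates separately at 360 days after HPE: native-liver survival whatever the bilirubin, and native-liver survival with total bilirubin below 1.5 mg/dL.
3. State which of the two endpoints the 68% describes.
4. For each hypothesis, restate the power or the smallest detectable absolute difference at its own control rate, for 23/56 and 29/70. Give the assumed IVIG rate explicitly as well as the relative gain.
5. If Aim 3 turns out to be low-powered estimation, say so plainly.

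The cost is one tabulation from a study the network already runs and one rewritten paragraph. The stated power may become less favourable. No extra infants are needed.
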